9.1 Primary Outcomes

The two primary outcomes for the trial will be: (a) spine-related cost of care at one year and (b) change in pain at three months as assessed by the Oswestry Disability Index (ODI, Appendix G). Secondary outcomes will include pain at 12 months, quality of life at 12 months assessed using the EQ-5D, and self-efficacy at 12 months assessed using a scale developed by Lorig et al. (31).

Table 2: Outcomes

Primary	Spine related cost of care at one year Change in pain (measured by ODI) at three months
Secondary	Change in pain (measured by ODI) at one year Quality of life (measured by EQ-5D) at one year Self-efficacy (measured by scale developed by Lorig et. al) at one year

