9.2.2 Self-Efficacy

We will evaluate self-efficacy at baseline, six months, and one year. As the focus of this trial is to support those with acute spine pain to prevent the development of chronic pain, measuring self-efficacy both as a predictor and outcome of the treatment arms will be necessary as a metric of self-management for future episodes. We will use Lorig et al.'s self-efficacy scale for individuals with musculoskeletal complaints, which has three subscales that focus on pain, functioning, and other symptoms (31). Because spine-specific pain is already captured with ODI, we will use the "functioning" and "other symptoms" subscales in this trial to measure self-efficacy (Appendix J). The "function" subscale produces an average of 73.27 (s.d. 20.22), and the "other symptoms" subscale produces an average of 55.62 (s.d. 21.64).

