10.1 Analysis plan

All analyses will be performed using intention to treat principles based on study arm with which a subject is assigned at study enrollment and regardless of whether or not all protocol steps have been completed. We will report means and frequencies of pre-randomization variables separately by study arm. Comparison of these values will be made with generalized estimating equations to adjust for the block and cluster randomized design.

Because cost data in healthcare is not normally distributed (32) due to significant zero data representing subjects for whom there is little to no cost, we will have to model the data accordingly. We will evaluate the two primary outcomes, total cost of care, using generalized estimating equations with gamma distributed errors and an identity link function which can account for a positively skewed distribution. Changes in ODI from baseline to three months will be compared for the treatment arms using generalized estimating with normally distributed errors and an identity link function. All models will adjust for age and sex, account for the cluster and block randomized study design and include fixed effects for the 3 different delivery networks that were used for recruitment. In secondary analyses, we will repeat our models adjusting for unmatched confounders that remained despite randomization. Our primary analyses will compare each of the two treatment arms separately with usual care (i.e., ICE compared with usual care and IPT with usual care). Because we are evaluating two primary

outcomes, we will use a Bonferroni-corrected two-tailed type 1 error of 0.025. Analysis of secondary outcomes will also be performed using generalized estimating equations with error distributions and link functions appropriate to the outcomes being evaluated.

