Missing data will be accounted for using multiple imputation (51), which has been determined an adequate strategy to minimize both false positive and false negatives in clinical trials. We will perform 20 imputations using Proc MI in SAS with a fully conditional specification. The following variables will be used to perform the imputation: age, study arm, study site, clinic, sex, race/ethnicity, BMI, exercise frequency at baseline, education level, employment status, smoking status, other medical conditions at baseline, number of medications used for spine pain at baseline, length of pain at baseline, number of previous pain episodes, STarT back score, baseline ODI, baseline self-efficacy, baseline EQ-5D, and scores for patient-reported outcomes at every follow-up timepoints (ODI, cost, Lorig self-efficacy scale, and EQ-5D).

As resource utilization and ODI were collected at multiple time points, we will also evaluate non-missing cost and ODI data from each time point using a repeated measures design. In specific, we will use generalized estimating equations, with link functions and error distributions appropriate to the study outcomes, to assess changes in outcomes over the 12 months of follow-up, while accounting for correlations in the repeated measurements. For spine-related health spending, these analyses will be conducted using the time intervals at which raw data were collected as well as after converting estimates to evenly-spaced months. Because cost data in healthcare is not normally distributed with zero values for participants with no resource utilization during follow-up, we will winsorize estimated costs at the 95th

percentile in secondary analyses. We will report relative spending differences with confidence intervals and a two-tailed p value. As a sensitivity analysis, we will conduct a complete-case analysis on all non-missing values.

Exploratory analyses will be performed evaluating the effect of the interventions on cost in various strata of clinical interest, including age, sex, STarT Back risk group, location of pain, and whether or not this was the subject's first pain episode. We will also evaluate the percentage of subjects in each arm with a decrease in ODI of six points at three, six, and twelve months of follow-up.

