Because cost data in healthcare is not normally distributed (32) due to significant zero data representing subjects for whom there is little to no cost, we will have to model the data accordingly. We will evaluate the two primary outcomes, total cost of care, using generalized estimating equations with Poisson distributed errors and a log link function which can account for a positively skewed distribution. Changes in ODI from baseline to three months will be compared for the treatment arms using generalized estimating with normally distributed errors and an identity link function. All models will adjust for age and sex, account for the cluster and block randomized study design and include fixed effects for the 3 different delivery networks that were used for recruitment. In secondary analyses, we will repeat our models adjusting for unmatched confounders that remained despite randomization. Our primary analyses will compare each of the two treatment arms separately with usual care (i.e., ICE compared with usual care and IPT with usual care). Because we are evaluating two primary outcomes, we will use a Bonferroni-corrected two-tailed type 1 error of 0.025. Analysis of secondary outcomes will also be performed using generalized estimating equations with error distributions and link functions appropriate to the outcomes being evaluated.

Missing data will be accounted for using multiple imputation (51), which has been determined an adequate strategy to minimize both false positive and false negatives in clinical trials. We will perform 20 imputations using Proc MI in SAS with a fully conditional specification. The following variables will be used to perform the imputation: age, study arm, study site, clinic, sex, race/ethnicity, BMI, exercise frequency at baseline, education level, employment status, smoking status, other medical conditions at baseline, number of medications used for spine pain at baseline, length of pain at baseline, number of previous pain episodes, STarT back score, baseline ODI, baseline self-efficacy, baseline EQ-5D, and scores for patient-reported outcomes at every follow-up timepoints (ODI, cost, Lorig self-efficacy scale, and EQ-5D).

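### The main models for one-year EQ-5D and self-efficacy do not name the outcome's own baseline as a covariate, although it is collected at month 0; adding it is a nearly free gain in precision on secondary outcomes

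*Combined protocol and SAP*

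**What the plan says.** - **Outcome definitions.** Protocol Table 2 and SAP Table 1 label the one-year ODI outcome "Change in pain (measured by ODI) at one year". The other two secondary outcomes are labelled "Quality of life (measured by EQ-5D) at one year" and "Self-efficacy (measured by scale developed by Lorig et. al) at one year". Whether these two are levels or changes is not made explicit.
- **Covariates.** Protocol 10.1 and the SAP analysis plan both state: "All models will adjust for age and sex, account for the cluster and block randomized study design". Fixed effects for the three delivery networks are added.
- **Secondary-outcome models.** "Analysis of secondary outcomes will also be performed using generalized estimating equations with error distributions and link functions appropriate to the outcomes being evaluated". This leaves the link and error distribution open and names no baseline term.
- **Baseline data.** Protocol Table 3 schedules EQ-5D and self-efficacy at month 0. Section 9.2.2 adds: "We will evaluate self-efficacy at baseline, six months, and one year". The imputation model includes "STarT back score, baseline ODI, baseline self-efficacy, baseline EQ-5D".
- **Other analyses.** As a secondary analysis, "we will repeat our models adjusting for unmatched confounders that remained despite randomization"; no variables are listed. The repeated-measures analysis covers cost and ODI only. Baseline variables will be reported by arm and compared with GEE.

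**The concern.** Both instruments have a baseline measurement, and the plan trusts those baselines enough to impute from them, yet it does not use them in the arm comparison. Imputing from a baseline value fills in missing outcomes; it does not adjust the treatment contrast.

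Two things follow if the one-year value is compared without its baseline. The confidence interval is wider than it need be, and part of any baseline difference between arms shows up as an apparent one-year difference.

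The design makes such gaps plausible. Only 33 clinics are randomized, the trial is open-label, and patients consent at clinics whose arm is already assigned. Study-recommended visits are free of out-of-pocket cost in ICE and IPT, while usual-care patients pay standard copayments (protocol 7.5). Who enrols could therefore differ by arm, so gaps might be systematic as well as due to chance. The documents give nothing with which to quantify that. Quality of life is part of the hypothesis in protocol section 3, so the EQ-5D comparison will be read closely.

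**Working it through.** **Inputs from the documents.** 1,032 per arm, 10% loss, 33 clinics in a 1:1:1 ratio (11 per arm), ICC 0.01 (stated for cost), self-efficacy SDs 20.22 (function) and 21.64 (other symptoms), and an EQ-5D minimal important difference of 0.08.

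**Assumptions.** ICC 0.01 also holds for these outcomes. The baseline-to-one-year correlation rho is 0.5, range 0.3 to 0.7. The EQ-5D SD is 0.15 to 0.20. Alpha is two-sided 0.05, since the plan assigns 0.025 only to the two primary outcomes. Blocking and network effects are ignored.

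**Step 1: the plan's own figure.** No sample size or power is given for EQ-5D or self-efficacy, so the cost calculation serves as a check on the method. With the SD proportional to each arm's mean (1.25 and 1.25 × 0.80 = 1.00):

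n0 = (1.25² + 1.00²)(1.960 + 0.842)² / 0.20² = 503 per arm.

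Evaluable per arm = 1,032 × 0.9 = 928.8; per clinic m = 928.8 / 11 = 84.4; design effect = 1 + 83.4 × 0.01 = 1.834.

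503 × 1.834 / 0.9 ≈ 1,025 per arm, within 1% of the stated 1,032.

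**Step 2: no baseline in the model.** In SD units, the between-clinic part is B = 0.01 and the within-clinic part is W = 0.99 / 84.4 = 0.01172.

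SE = SD × √[(2/11)(B + W)] = 20.22 × √[(2/11)(0.02172)] = 1.27 points (function), or 1.36 (other symptoms).

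Difference detectable with 80% power = 2.802 × SE = 3.56 points (function), or 3.81 (other symptoms).

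**Step 3: baseline added (function subscale).** Three cases:

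- (a) Clinic-level correlation equals rho: variance × (1 − rho²).
- (b) Baseline predicts only within clinics, and the clinic mean of baseline is also in the model: B + W(1 − rho²).
- (c) Baseline predicts only within clinics, with the subject-level covariate alone: B(1 + rho²) + W(1 − rho²), because the common slope is then wrong between clinics.

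| rho | (a) SE, power at 3.56 | (b) SE, power | (c) SE, power |
|---|---|---|---|
| 0.3 | 1.21, 84% | 1.24, 82% | 1.27, 80% |
| 0.5 | 1.10, 90% | 1.18, 85% | 1.26, 81% |
| 0.7 | 0.91, 98% | 1.09, 90% | 1.25, 82% |

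The comparison without baseline has 80% power at 3.56 points by construction. In case (a) at rho = 0.5 the detectable difference falls to 2.802 × 1.10 = 3.08 points.

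**Step 4: carry-over of a chance gap.** The SD of a chance baseline gap between two arms is √[(2/11)(0.02172)] = 0.063 SD units, so a gap of 0.10 SD or more (either direction) occurs in about 11% of randomizations. In case (a), given a gap g, the one-year level difference under no effect is normal with mean rho × g and SD 0.063 × √(1 − rho²).

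For g = 0.10 on the function subscale, the shift is rho × 0.10 × 20.22 = 0.6, 1.0 or 1.4 points at rho = 0.3, 0.5 or 0.7. The chance of a false positive given that gap is 6.5%, 9.0% or 11.8%. Given no gap it is 4.0%, 2.4% or 0.6%. Averaged over randomizations it is 5%.

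**Step 5: EQ-5D.** With SD 0.20 the SE is 0.20 × 0.063 = 0.013, and unadjusted power for 0.08 exceeds 99.9%. At the edge of the 95% range of chance gaps (1.96 × 0.0126 = 0.025), the carry-over at rho = 0.7 is 0.017, well under 0.08.

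**Step 6: a plain change score.** In case (a) its variance relative to the level is 2(1 − rho) = 1.4, 1.0 or 0.6. The baseline-adjusted model gives 1 − rho² = 0.91, 0.75 or 0.51, which is lower each time.

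**The case against.** The best defence has four parts.

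**The plan does allow for imbalance.** It reports and compares baseline values by arm and repeats the models with adjustment for imbalanced confounders. That stands in part: a reader might infer that the plan makes no allowance at all for where the arms started, and that is wrong. But the re-analysis is secondary, lists no variables, and depends on what imbalance is seen, so it does not replace a covariate named in advance.

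**The outcomes may be meant as changes.** The prose of protocol 9.1 speaks of pain at 12 months alongside quality of life at 12 months, while Table 2 calls that same pain outcome a change; section 9.2.1 discusses EQ-5D in terms of change. This stands: a level-only definition cannot be treated as settled. It does not remove the point, because no baseline covariate is named on either reading and, by Step 6, the adjusted model is more precise than both.

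**There is no inflated error rate.** A reader might take the 9% in Step 4 to mean that the test is invalid. It does not mean that. The figure is conditional on a chosen gap; the rate is about 2.4% when there is no gap and 5% overall. This stands in full for chance gaps.

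**The gain may be small.** This stands too. It depends on an assumed correlation and a borrowed ICC, and in case (c) it nearly vanishes. The 3.56-point reference is only the detectable difference under these assumptions; the documents give no important difference for self-efficacy.

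**Conclusion.** The point holds as a free improvement on secondary outcomes, of low to moderate severity. The main models omit a baseline covariate that is already collected, and nothing else in the plan supplies it in advance.

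For self-efficacy function, the standard error falls from 1.27 to 1.10 points at rho = 0.5 (1.21 to 0.91 over 0.3 to 0.7) if clinic-level correlation equals rho. It is 1.18 if baseline predicts only within clinics and the clinic mean is included, and close to unchanged without that term. For EQ-5D, the effect on conclusions about the 0.08 benchmark is small at the assumed SDs.

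The documents do not support the stronger conclusion that the secondary results would be biased. Bias would require systematic baseline differences from enrolment after clinic allocation, which is possible here but not quantified. No primary outcome, sample size or primary error control is affected.

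**What to change.** In protocol 10.1 and the SAP analysis plan, after the sentence on secondary outcomes, add: *The models for EQ-5D and for each self-efficacy subscale will use the one-year value as the dependent variable and will include the subject's baseline value of the same measure as a covariate.* This also settles whether the outcome is a level or a change.

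Optionally add the clinic mean of that baseline. It protects the gain when baseline predicts differently within and between clinics, and it costs one between-clinic degree of freedom per model.

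An unadjusted change score is not a substitute: with equal clinic-level correlation it is less precise than the level when rho is below 0.5.

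The cost is one sentence in each document. No new data are needed, since both baselines are collected at month 0 and already used for imputation.

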10.2 Sample size

The ICE model was anticipated to reduce total cost of care by 25% compared to usual care (52–54). Because of the lack of peer-reviewed literature evaluating the economic impact of IPT, an effect similar to ICE was assumed for the purpose of performing power calculations. We will need to enroll a total of 3,096 patients (1,032 per arm) to conservatively detect a change in spending of 20% between either treatment arm and usual care with 80% power and an alpha of 0.05, with 33 clusters, and 10% loss to follow-up over the 12-month study period. Our results are robust to a standard deviation of 1.25 times the mean and an ICC value of 0.01. Given the substantially larger sample size required for our economic analyses, we powered our trial on the basis of this outcome, which would also give us more than 98% power to detect a 6-point change in ODI between each intervention arm and the usual care arm.

11. Risk Protection

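### The cost outcome is sized at alpha 0.05 but tested at a fixed 0.025, so its power is about 72% rather than 80%; Holm over the two outcomes within each comparison recovers most of the loss when ODI also shows an effect

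*Combined protocol and SAP*

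**What the plan says.** Protocol 9.1 names two primary outcomes: spine-related cost at one year and change in ODI at three months. Protocol 10.1 then sets two primary contrasts: "Our primary analyses will compare each of the two treatment arms separately with usual care", that is, ICE against usual care and IPT against usual care. The plan therefore has four primary tests.

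The only multiplicity rule is in protocol 10.1, repeated in the SAP (Statistical considerations, 1 Analysis plan): "Because we are evaluating two primary outcomes, we will use a Bonferroni-corrected two-tailed type 1 error of 0.025". The reason given is the number of outcomes. Neither document says whether the 5% is meant for each comparison or for the whole trial, and neither gives a step-down rule or an order of testing.

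Protocol 10.2 and the SAP sample-size section size the trial on cost, with 1,032 patients per arm for a 20% change in spending, "with 80% power and an alpha of 0.05, with 33 clusters, and 10% loss to follow-up". The variance inputs are "a standard deviation of 1.25 times the mean and an ICC value of 0.01". The same section adds that this size gives "more than 98% power to detect a 6-point change in ODI" between each intervention arm and usual care.

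**The concern.** The planning alpha and the testing alpha differ. A trial sized for 80% power at 0.05 has less than 80% when the test runs at 0.025, and the outcome affected is the one that set the sample size.

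The form of the correction makes this loss larger than it need be. Single-step Bonferroni holds cost at 0.025 even after ODI has been declared significant in the same comparison. Holm gives the same 5% guarantee over those two outcomes and releases the full 0.05 to the second test once the first is rejected. At stake is a real 20% cost difference being missed in roughly 28% of trials instead of 20%.

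The plan is also silent on what the 5% refers to, so a reader cannot tell which error rate stands behind a claim for one arm.

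**Working it through.** **Inputs from protocol 10.2 and 7.1.** 1,032 per arm; 10% loss, leaving 1,032 × 0.90 = 928.8 analysed; 33 clinics allocated 1:1:1, so 11 per arm; ICC 0.01; SD 1.25 times the mean; cost difference 20%. **Assumed, because the documents do not give them:** ODI SD of 20 with the same design effect as cost; correlation between the cost and ODI statistics of 0 to 0.5; equal clinic sizes; normal approximation.

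**Step 1: reproduce the plan's figure.** Set the usual-care mean at 1 and the intervention mean at 0.80, so the SDs are 1.25 and 1.00.
- Effective n needed at alpha 0.05: (1.960 + 0.842)² × (1.25² + 1.00²) / 0.20² = 502.8.
- With 11 clinics fixed, n = 502.8 × [1 + (n/11 − 1) × 0.01], so n = 917. Dividing by 0.90 gives 1,019 per arm, against 1,032 stated (1.3% apart).
- At the stated size: design effect 1 + (928.8/11 − 1) × 0.01 = 1.834; effective n 928.8/1.834 = 506; z = 0.20 / √(2.5625/506) = 2.81; power at 0.05 = Φ(2.81 − 1.96) = 80.3%.

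A common SD of 1.25 in both arms does not reproduce the plan: it gives 1,524 per arm.

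**Step 2: power at the level used for testing.** At 0.025 the critical value is 2.241, so power = Φ(2.81 − 2.241) = 71.6%. Reaching 80% at 0.025 would take about 1,500 per arm. At the anticipated 25% effect, z = 0.25 / √((1.25² + 0.9375²)/506) = 3.60 and power at 0.025 is 91%.

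**Step 3: Holm within one comparison.** Cost is rejected if p ≤ 0.025, or if p ≤ 0.05 and ODI has p ≤ 0.025. With uncorrelated outcomes, cost power = 0.716 + (0.803 − 0.716) × (ODI power at 0.025). The ODI z is d / (20 × √(2/506)).

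| ODI effect | ODI z | ODI rejection at 0.025 | Cost power, fixed 0.025 | Cost power, Holm within comparison |
|---|---|---|---|---|
| 6 points | 4.77 | 99.4% | 71.6% | 80.2% |
| 3 points | 2.39 | 55.8% | 71.6% | 76.4% (75.1% at correlation 0.5) |
| none | 0 | 2.5% | 71.6% | 71.8% |

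If ODI power is only 98% at 0.05 (z = 4.01), ODI rejects 96.2% of the time at 0.025 and cost power is 79.9%.

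**Step 4: error rates.**
- Within one comparison, both outcomes null and uncorrelated: 1 − 0.975² = 4.9%, under either rule.
- Across both comparisons, everything null: 1 − 0.975⁴ = 9.6% if the four tests were independent. With the shared usual-care arm (correlation 0.5 between contrasts), simulation gives 9.1%, falling to 8.5% at outcome correlation 0.5. This too is the same under either rule.
- ODI effects of 6 points in both arms and no cost effect in either: the chance of at least one false cost claim is about 4.7% under fixed 0.025 and 9.0% under Holm within each comparison (simulation).

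**Step 5: Holm over all four tests, for reference.** Simulated trial-wide error stays below 5% (4.7% when everything is null and the outcomes are uncorrelated). Cost power becomes about 77% if all four effects are real, about 70% with 3-point ODI effects, 65% if both arms lower cost and ODI is null, and 66% if only one arm works.

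**The case against.** **The present rule is valid as it stands.** ICE and IPT are distinct interventions, each compared separately with usual care. Many statisticians treat such comparisons as separate families, and on that view 4.9% per comparison is proper control. This stands. A reader might infer from the four tests and the 9% figure that the plan must correct across all four. The documents set no trial-wide error target, and adjusting across two different treatments is a design choice.

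**No single rule does everything.** A reader might infer that Holm would both bring trial-wide error to 5% and restore the lost power. Within-comparison Holm leaves trial-wide error at about 9%. Four-test Holm controls it but recovers only part of the power, and lowers cost power below the present 72% when ODI is null or only one arm works.

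**The 80% figure depends on ODI.** The statement in 10.2 is conditional: power if a 6-point difference exists. The plan forecasts an effect for cost only; 6 points is the change it calls clinically meaningful. It would be wrong to read 10.2 as expecting ODI to succeed 98% of the time, hence the 3-point and null rows above.

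**The loss matters less at the anticipated effect.** At 25%, power at 0.025 is about 91%. The 72% applies to the 20% effect that the plan chose as conservative, and it arises from the mismatch between planning and testing alpha.

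**Holm has costs.** False cost claims rise when ODI is real and cost is null. Bonferroni has matching 97.5% intervals, whereas Holm has no equally simple simultaneous ones. A three-month ODI p-value between 0.025 and 0.05 cannot be settled until one-year cost is known. All of this is true. These costs are small, and the plan should state them.

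**Conclusion.** The concern holds as a power point with an available remedy. As written, each comparison has about 72% power for the 20% cost effect that the plan says it can detect with 80%. Holm over the two outcomes within each comparison keeps 5% per comparison, is never less powerful than the present rule, and raises cost power to about 80%, 75–76% or 72% for ODI effects of 6, 3 or 0 points.

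The 80.3% and 71.6% rest on the plan's own inputs, with each arm's SD taken as 1.25 times its own mean, the reading that comes within 1.3% of the stated sample size. The Holm figures rest also on the assumed ODI SD and design effect. Outcome correlation moves them by little more than one point. The error figures assume a correlation of 0.5 between the two contrasts, from equal allocation with a shared control.

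The documents do not support the stronger conclusion that the Bonferroni rule is invalid or that a four-test correction is required. What is missing is a statement of which error rate is being controlled.

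**What to change.** In protocol 10.1 and the SAP (Statistical considerations, 1 Analysis plan), replace the fixed 0.025 as follows: within each comparison with usual care, test the two primary outcomes by Holm at 0.05. The smaller p-value is compared with 0.025 and, if it is significant, the larger with 0.05.

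Add that error is controlled at 5% per comparison and that the chance of at least one false primary claim across both comparisons can reach about 9%. State how intervals will be reported (for example, unadjusted 95% intervals labelled as such, or 97.5% intervals alongside the Holm decisions), and that an ODI p-value between 0.025 and 0.05 stays open until the one-year cost result is available.

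In 10.2 and the SAP sample-size section, give cost power at the level used for testing: about 72% at fixed 0.025 for a 20% effect, with the Holm figures and their ODI assumptions beside it.

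If the investigators want one trial-wide 5% claim, Holm over all four tests is the alternative, and they should accept its cost power of about 65% to 77% knowingly.

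The change needs no further patients or data, only wording, together with the small downsides set out above.

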5.1. Inclusion Criteria

- Patients with back or neck pain of ≤ 3 months' duration. All patients must have spine pain with or without radiation to the extremities or the head
- Age ≥ 18 years
- Willing and able to provide informed consent

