9.1.2 Pain

The ODI is the most commonly used scale for low back pain (35). It is a self-administered questionnaire that has ten topics: intensity of pain, lifting, sexual function, social life, sleep, and ability to walk, sit, stand, care for oneself, and travel. It has been recommended as one of the standardized metrics for research of low back pain based on its ability to quantify functional

status in this population (36). The ODI typically takes three to five minutes to complete, and one minute to score (37). Previous studies have evaluated the ODI in pain-free subjects and found that mean score to be 10.19 (35, 38, 39) and those with disability from low back pain is 22.07 (40). Previous studies have indicated that a change in ODI by 6 points is clinically meaningful (41).

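### Location of pain is a prespecified stratum for cost but not for the co-primary ODI, and it is missing from the imputation list, so ODI differences between back and neck pain would be examined only post hoc and imputed data would blur them

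*Combined protocol and SAP*

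**What the plan says.** **Population and outcome.** The first inclusion criterion (protocol 5.1) opens "Patients with back or neck pain of" up to three months' duration and does not restrict entry to the low back. Protocol 9.1 and the SAP's primary outcomes section name "change in pain at three months as assessed by the Oswestry Disability Index" as one of two primary outcomes for everyone.

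**Support for the instrument.** Protocol 9.1.2 (SAP 1.2) begins "The ODI is the most commonly used scale for low back pain". Its reference mean for people with disability (22.07) comes from low back pain. The 6-point meaningful change is cited to a trial whose title, in the reference list, concerns recent-onset low back pain. In protocol Table 3, the ODI is the only health-status measure scheduled at month 3 (EQ-5D is at 0, 1.5, 6 and 12 months; self-efficacy is at 0, 6 and 12). No neck instrument is scheduled.

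**Use of location.** In protocol 10.1 and the matching SAP text, location appears only in the exploratory analyses "evaluating the effect of the interventions on cost in various strata of clinical interest, including age, sex, STarT Back risk group, location of pain" and first pain episode. The three ODI analyses have no location term:
- the primary model adjusts for age, sex, the design and delivery network;
- the responder analysis reads "We will also evaluate the percentage of subjects in each arm with a decrease in ODI of six points";
- the longitudinal analysis reads "we will also evaluate non-missing cost and ODI data from each time point using a repeated measures design".

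**Imputation list.** Both documents list the variables. The pain-related run is "length of pain at baseline, number of previous pain episodes, STarT back score, baseline ODI, baseline self-efficacy, baseline EQ-5D", followed by outcome scores at every follow-up. Location of pain is not there. Study site is listed next to clinic and means where the subject was recruited, not the part of the spine.

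**The concern.** The plan treats location of pain as clinically important for cost, yet not for the endpoint where it bears most directly on measurement. If the ODI responds less in neck pain, the pooled three-month contrast understates the effect in back pain. A back-only ODI result produced after a disappointing pooled result would carry little weight, whereas a prespecified one could be read at face value as exploratory evidence.

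The imputation gap affects an analysis that is already planned. When cost is compared within location strata on imputed data, the imputed values know the subject's arm but not the location. They therefore carry the pooled arm effect into both strata and make back and neck look more alike than they are.

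**Working it through.** **1. Strata against the imputation list (protocol 10.1 and SAP analysis plan)**

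| Named stratum | Counterpart in imputation list |
|---|---|
| Age | Age |
| Sex | Sex |
| STarT Back risk group | STarT Back score |
| First pain episode or not | Number of previous episodes |
| Location of pain | None |

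**2. Shrinkage from imputing without location.** Let m be the missing share (equal in both strata), and let Db, Dn and Dp be the arm effects in back, neck and pooled. If imputed values carry only Dp, the stratum estimates are (1 − m)Db + mDp and (1 − m)Dn + mDp. Their difference is (1 − m)(Db − Dn).
- With m = 0.10, the plan's 12-month loss, an assumed 6-point difference becomes 6 × 0.90 = 5.4.
- This is a ceiling. Baseline ODI and ODI at other visits are in the list and can carry part of the location signal.
- Missingness of three-month ODI is not stated.
- Adding location as a main effect alone would not cure this. Imputed values would still carry one common arm effect, so the arm-by-location term is needed.

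**3. The plan's own ODI power figure.** The sample size section claims more than 98% power for 6 points but gives no ODI standard deviation (SD), so the figure cannot be reproduced. It can be bounded. Inputs are 1,032 × 0.9 = 929 completers per arm, 11 clinics per arm, and the ICC of 0.01 that the plan gives for cost.
- Mean cluster size: 929/11 = 84.4. Design effect: 1 + 83.4 × 0.01 = 1.834.
- SE = SD × √(2 × 1.834/929) = 0.0628 × SD.
- At two-sided 0.025 by normal approximation, 98% power needs SD ≤ 6/(0.0628 × (2.241 + 2.054)), about 22. At 0.05 the limit is about 24.

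**4. Possible dilution (assumed inputs).** Let q be the neck-only share and r the ODI response in neck pain relative to back pain. Neither is in the documents. Pooled effect = 6 × (1 − q(1 − r)). Power is at two-sided 0.025 with the variance above and 20 degrees of freedom.

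| q | r | Pooled effect | Power, SD 15 | Power, SD 20 |
|---|---|---|---|---|
| 10% | 0.5 | 5.7 | >99% | 98% |
| 30% | 0.5 | 5.1 | >99% | 94% |
| 30% | 0 | 4.2 | 97% | 81% |
| 40% | 0 | 3.6 | 91% | 67% |

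**5. What an ODI-by-location analysis could show.** Location varies within clinic, so SE(interaction) ≈ SD × √(2 × 0.99/929 × (1/q + 1/(1 − q))). At q = 30% this is 1.51 (SD 15) or 2.01 (SD 20).
- A 6-point back-minus-neck difference (r = 0) has 98% or 85% power at two-sided 0.05.
- A 3-point difference (r = 0.5): 3/1.51 = 1.99 gives about 51%, and 3/2.01 = 1.49 gives about 32%.
- The 95% confidence interval half-width for the neck-stratum effect is about 2.8 or 3.7 points. At q = 20% it is about 3.3 or 4.4.

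**The case against.** Four counter-arguments deserve weight.

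**The information is not lost.** A reader might infer that dilution could be neither seen nor estimated. The documents do not support that. Location must be recorded for the cost strata, the ODI is scheduled for everyone, and both the repeated-measures and the complete-case analyses use observed data. The half-widths in step 5 show that a location-specific estimate is feasible. What is missing is prespecification.

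**Dilution is assumed.** The ODI topics listed in protocol 9.1.2 include pain intensity, lifting, sleep, social life and travel, so zero response in neck pain is hard to credit. Protocol 9.2.2 treats the ODI as capturing spine pain generally. Appendix G was not among the supplied text, so neck-adapted wording cannot be excluded. This stands: the table in step 4 shows a range, not a finding.

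**Falling below 6 points is not failure.** A reader might take a pooled effect of 5.1 as missing the plan's threshold. Six points is a meaningful change, a responder cut-off and the power alternative. The between-arm test is against zero, and power at 5.1 points stays at 94% or more for SD 15 to 20. Moderate dilution would seldom produce a null result by itself.

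**The trial's target is all acute and subacute spine pain.** The pooled analysis is the right primary one for that target, and nothing here shows it to be biased. This also stands, and it is why the remedy leaves the primary analysis alone.

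None of these arguments explains why location is stratified for cost but not for the ODI, or why it alone has no counterpart among the imputation variables.

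**Conclusion.** The point holds as a gap in prespecification and in the imputation model. Any ODI-by-location result under the current text would be post hoc. Imputed data would shrink arm-by-location contrasts, for the planned cost analysis and for any ODI analysis, by at most about the missing share. That is about 10% if the 12-month loss figure applies, and less where other time points help. This assumes equal missingness across locations and an imputation model without location.

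Dilution of the pooled ODI effect is plausible but not demonstrated. Its size depends on neck share, ODI SD and ODI response in neck pain, none of which the documents give. The documents do not support a claim that the primary ODI comparison is invalid or underpowered on this ground.

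**What to change.** Keep the instrument and the all-subject primary analysis. In protocol 10.1 and the matching SAP analysis plan:

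1. Add location of pain and its interaction with study arm to the imputation model, or impute separately by arm with location included.
2. Extend the exploratory location stratum to three-month ODI change, with an arm-by-location term and location-specific estimates with confidence intervals. State how subjects with both back and neck pain are classified. Label this an exploratory subgroup analysis: a back-only effect answers a different question from the pooled one, so it is not a sensitivity analysis.

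The cost is two changes to the text and one extra model on data already collected. The back-only estimate is less precise than the pooled one. Interaction power is limited if the ODI response in neck pain is only partly reduced: roughly 30–50% for a 3-point difference at an assumed 30% neck share and SD 20 to 15. The estimates and intervals should therefore be reported rather than relying on the interaction test.
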